 - Deliver 0.625 ml/kg/hour (equivalent to 6.25 mg/kg/hour or 150 mg/kg/day)
 - Resulting final rate (>1 ml/hour, depending on weight) is sufficient to keep intravenous line open

	Pre-	Days	s Post	t-KP	Weeks Post-KP							Months of Life		
	KPa	3 ^{b,c}	7	10	2	4	8	12	18	24	12	18	24	
Demographic data														
TSBAs														
Bc														
AST/ALT														
GGT														
Albumin														
Sodium														
Total Bilirubin														
Platelets														
INR														
25-hydroxy Vitamin D														
Vitamin A														
Vitamin E														
Weight														
Sentinel/Adverse events														

v. Observations for this study, performed as part of standard clinical care

^aDrawn within seven days of KP

^bIf laboratory adverse event occurs (see Table 4), will perform an additional measurement 5 days post-KP ^cAny "days post-KP labs (3,7,10) drawn outside of the outlined visit point will not be considered a deviation if +/- 2 days. For "weeks post-KP" labs (2,4,8,12,18,24) +/- 7 days window and "months of life" labs (12,18,24) +/-2 weeks window.

- a) Primary outcomes:
 - Any normal TSBA (0-10 umol/L) in the first 24 weeks after KP
- b) Secondary outcomes:
 - Trajectory of TSBAs changes over study period
 - Trajectory of Bc changes over study period (drawn as part of liver panel)
 - Trajectory of AST and ALT changes over study period (drawn as part of liver panel)
 - Trajectory of GGT changes over study period (drawn as part of liver panel)
 - Trajectory of albumin changes over study period (drawn as part of liver panel)

- Trajectory of sodium changes over study period (drawn as part of chemistry panel)
- Trajectory of Total Bilirubin changes over study period
- Trajectory of platelets changes over study period (drawn as part of complete blood count)
- Trajectory of INR changes over study period
- Trajectory of 25-hydroxy Vitamin D concentrations over study period and correlate with fat-soluble vitamin supplementation
- Trajectory of Vitamin A concentrations over study period and correlate with fat-soluble vitamin supplementation
- Trajectory of Vitamin E concentrations over study period and correlate with fat-soluble vitamin supplementation
- Trajectory of weight z-score changes over study period (to detect fluid overload during the infusion period and growth effects at later times)

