Historical controls from the START clinical trial will be used for the primary outcome, as this is the only systematic examination of TSBAs after KP.⁴ In the START trial, subjects receiving a KP between 2005-2011 were enrolled and TSBAs drawn as many as eight times (pre-KP; 1, 2, 3, and 6-months post-KP; and 12, 18, and 24 months post-KP). We will examine these results to determine the number of subjects with normal TSBAs after six months. We expect a maximum of 5% of subjects to have normalized TSBAs, based on a recent publication of correlating TSBAs from the START trial with fat-soluble vitamin levels (118 data points taken at 1, 3, or 6 months post-KP) (Figure).⁵

For secondary outcomes, results will be compared to previously published findings and results from our institution. For example, laboratory and clinical two-year outcomes for BA have been described previously, for all infants receiving KP and those with total bilirubin <2 mg/dL vs. \geq 2 mg/dL within 3 months of KP.^{3,36} In addition,

of the patients receiving a KP at our institution between 2007-2014, only 1/48 (2.1%) had a normal Bc recorded in the first two weeks post-KP.

One limitation of this approach is that using historical controls can lead to a type 1 error, because BA management has evolved over time. For example, newborn screening now allows for earlier diagnosis and treatment with the KPs. In addition, at our center intramuscular Vitamin A is now used to correct Vitamin A levels quickly, alongside the oral fat-soluble vitamin preparations used in the past. Finally, nutritional approaches have changed, including use of early parenteral nutrition immediately after KP. These changes may alter outcomes independent of intravenous NAC treatment.

ii. Sample-Size Calculations

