Simon's two-stage "minimax" design will be used to calculate sample sizes for the primary outcome.²⁹ The null hypothesis will be tested against a one-sided alternative. Assuming a normalization rate of approximately 5% (see above), the null hypothesis is that the true response rate is 5% for normalization of TSBAs 24 weeks after KP. In the first stage, 12 patients will be accrued. If no patient normalizes TSBA within 24 weeks of KP, the study will be stopped. Otherwise, 4 additional patients will be accrued for a total of 16. The null hypothesis will be rejected if \geq 3 of 16 patients normalize TSBA within 24 weeks of KP. This design yields a type I error rate of 5% and power of 80% when the true response rate is 25%. Subjects that do not complete the 7 day NAC infusion after the Kasai operation and 24 weeks of follow up may be replaced at the discretion of the PI/IND Sponsor.

G. Ethical Issues

i. Informed Consent

Participants will only be enrolled after their parent(s)/guardian(s) understand the nature and objectives of the trial, as well as the attendant risks and possible discomforts. All families will be given a consent form describing NAC and possible side-effects (see Consent in appendix).

ii. Children as Research Subjects

NAC may benefit patients with BA by improving bile flow after KP. This study does have risks. Intravenous NAC has been studied extensively in pediatric populations. NAC side effects include anaphylaxis reactions, generalized urticaria, hives, rash, stomatitis, rhinorrhea, and vomiting. These side effects are most often reported at the beginning of NAC infusion for acetaminophen toxicity, when higher doses than used in this study are administered.

This study also involves an intravenous line for NAC administration and blood draws. The intravenous line is routinely placed pre-operatively to deliver fluids when enteral feeds must stop. The same intravenous line will be used for NAC administration. The only instance in which an additional peripheral intravenous line will be placed is if intravenous access is lost during the seven-day period of NAC treatment. All blood draws for this study will be part of routine clinical care, and would be performed independent of participation in this trial.

H. Pharmaceutical Information

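### The 5% type I error holds only if about 5% or fewer untreated infants ever reach a normal TSBA by 24 weeks, and the cited source for 5% does not clearly measure that rate

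*Combined protocol and SAP*

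**What the plan says.** Section D.v defines the primary outcome as "Any normal TSBA (0-10 umol/L) in the first 24 weeks after KP". This is a cumulative, per-infant endpoint, and both decision rules in F.ii (stop if none of the first 12 respond; reject the null at 3 or more of 16) also count normalization at any time within 24 weeks. F.ii words the null slightly differently: "the null hypothesis is that the true response rate is 5% for normalization of TSBAs 24 weeks after KP". It states a type I error of 5%, and power of 80% at a true rate of 25%.

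The 5% comes from F.i: "We expect a maximum of 5% of subjects to have normalized TSBAs, based on a recent publication of correlating TSBAs from the START trial". The source is described as "118 data points taken at 1, 3, or 6 months post-KP". START itself had "TSBAs drawn as many as eight times (pre-KP; 1, 2, 3, and 6-months post-KP", with later draws to 24 months. F.i adds: "We will examine these results to determine the number of subjects with normal TSBAs after six months". It gives no result of that count and does not say what follows if it differs from 5%. Its caveat on historical controls reads: "One limitation of this approach is that using historical controls can lead to a type 1 error, because BA management has evolved over time". The examples given are newborn screening, vitamin A injections and nutrition.

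**The concern.** The null rate and the endpoint should describe the same event in the same unit. The endpoint asks whether an infant was ever normal by 24 weeks. The cited data are values at separate times, and the text does not say how many infants supplied them or how many values were normal. On its plain reading, the promised START count of subjects normal after six months is a narrower event than ever normal by 24 weeks, and would set the benchmark too low.

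The comparison with 5% is the trial's only formal efficacy decision, and it settles whether NAC goes on to further study. A reader who sees 3 of 16 needs to know how often that would occur without NAC, and the text does not supply the rate needed to say so. The caveat in F.i concerns changes in care, not this mismatch. A related gap is that START was a randomized trial of corticosteroids (title of reference 4) and steroids are not standard care here (D.vii), yet the text names no START arm as the source of the 5%.

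**Working it through.** **Inputs.** From F.ii: 12 infants in stage 1, stop at 0 responders; 4 more infants; reject at 3 or more of 16; null 5%, alternative 25%. From D.v: the endpoint and visit windows. From F.i: the START schedule and the 118 points.

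**Formula.** With X1 ~ Bin(12, p) and X2 ~ Bin(4, p),

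P(reject) = P(X1=1)·P(X2≥2) + P(X1=2)·P(X2≥1) + P(X1≥3).

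**Step 1: reproduce the plan.**

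- p = 0.05: 0.3413×0.0140 + 0.0988×0.1855 + 0.0196 = 0.0048 + 0.0183 + 0.0196 = 0.0427.
- p = 0.25: 0.1267×0.2617 + 0.2323×0.6836 + 0.6093 = 0.0332 + 0.1588 + 0.6093 = 0.8013.

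The stated 5% and 80% are correct as limits. A grid search also returns this design as the minimax one.

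**Step 2: the same rule at other untreated rates.** Setting P(reject) = 0.05 gives p = 0.0533. The rates above 5.33% are illustrative; none is in the documents.

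| Untreated ever-normal rate | Type I error |
|---|---|
| 5% | 4.3% |
| 5.33% | 5.0% |
| 6% | 6.7% |
| 7.5% | 11.3% |
| 10% | 21.0% |

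**Step 3: direction of the mismatch.** For an infant seen at every visit, the ever-normal indicator is at least the average of that infant's per-visit indicators. Averaged over such infants, the ever-normal rate is at least the mean per-visit rate. The two are equal when the same infants are normal at every visit, so the gap may be zero.

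**Step 4: what 118 points can settle.** Assume, for this step only, that the 5% refers to data points and that each infant gives at most one point per time.

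- Number of infants: 118/3 rounded up = 40, up to 118. Normal points: 0.05×118 = 5.9, so at most 5.
- Lowest rate with 5 normal points: 2 infants supply all 5 and 113 others supply one each. 2/115 = 1.7%, error 0.2%.
- Highest rate: 5/40 = 12.5%, error 32.1%.
- With 2 or fewer normal points, the rate in these infants is at most 2/40 = 5.0% and the error at most 4.3%.
- If all 118 were different infants and 5 were normal: 4.2% (exact 95% CI 1.4% to 9.6%), error 2.8% (0.1% to 19.3% over the interval). The ever-normal rate would then not have been observed at all.

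If instead the 5% is a true ceiling on infants ever normal, the error is at most 4.27%.

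**Step 5: schedules.** START's 2-month draw is not among the 118 points; adding it can raise the ever-normal count but not lower it. START's 6-month draw falls at about 365.25/2/7 = 26.1 weeks, while the last draw here is at 24 weeks with "labs (2,4,8,12,18,24) +/- 7 days window", so at most week 25. That works slightly the other way.

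**The case against.** The strongest reply is that F.i speaks of a maximum and of subjects. Read literally, 5% is already a per-infant ceiling, and the attained error of 4.27% is within the stated 5%. The number of infants, the count of normal values and the arm may be in the figure, which is not shown, or in the cited publication. Section B says the operation occasionally normalizes bile flow, which fits a small group of infants who stay normal and little gap between per-visit and ever-normal rates. The plan also promises a per-subject START count, and after six months can be read as once six months have passed, which is close to the endpoint.

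Much of this stands. A reader might infer from the calculations that the true type I error is 11% to 32%. The documents do not support that: those figures need the 5% to refer to points rather than subjects, and 32% also needs the fewest possible infants with every normal point in a different one. A reader might also infer from the F.ii wording that the null is a fixed-time rate; since the endpoint and both decision rules are any-time, this is a wording point only.

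What does not stand is that the text makes the link. It reports no ever-normal proportion, the promised count needs a generous reading to fit the endpoint, and no consequence for the stated error is given.

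**Conclusion.** The concern holds as a missing justification, not as a demonstrated error. The stated 5% depends on an untreated ever-normal rate of about 5% or less, and an excess of only 0.33 percentage points uses up the margin. Whether the real rate lies above or below 5.33% cannot be determined from the documents. The direction in step 3 assumes infants observed at every visit, and the bounds in step 4 rest on the assumptions stated there. This is a cheap improvement: the plan already intends to count START infants, and a count that matches the endpoint would tell readers what 3 of 16 can support.

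**What to change.** 1. In F.i, replace the planned START count of subjects normal after six months with the number and proportion of START infants having at least one TSBA of 0-10 umol/L at the 1, 2, 3 or 6-month draws. Give the numerator, denominator and exact 95% confidence interval, overall and by START treatment arm.
2. Handle deaths, transplants and missed draws in START by the same rule as for this trial's infants, and show the result with and without infants lacking full follow-up. F.ii leaves replacement of infants without 24 weeks of follow-up to discretion, so that rule has to be written down first. Fix all definitions before the tabulation is run, and without reference to this trial's responses.
3. In F.ii, word the null as at least one normal TSBA within 24 weeks. Keep the 0 of 12 and 3 of 16 rules. Report their exact type I error at the START proportion and over its interval, and do not claim a 5% test if that error is above 5%.

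The cost is one tabulation of data the plan already says it will examine, plus wording. No samples, visits or decision rules change. The downsides are a possibly less favourable stated error and a wide interval, especially by arm. With an assumed 59 infants, 3 ever normal is 5.1% (exact 95% CI 1.1% to 14.1%) and an error of 4.45% (0.1% to 39.8% over the interval); 4 ever normal is 6.8% and an error of 8.9%.

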 - a) Age less than or equal to 90 days at time of KP (standard age range in which KPs are performed)
 - b) BA diagnosis made by intraoperative cholangiography and KP performed at Texas Children's Hospital, Texas Medical Center Campus
 - c) Legal guardian(s) sign consent after understanding risks and investigational nature of study

ii. Exclusion Criteria

- a) Decompensated liver disease (INR >1.3) despite parenteral Vitamin K administration
- b) KP not performed for any reason (i.e., normal intraoperative cholangiography, or liver found to be too diseased intraoperatively to proceed with KP)
- c) Active respiratory infection
- d) Renal impairment, as defined by having an eGFR < 60 mL/min/1.73m² or creatinine clearance < 60 mL/min (https://www.niddk.nih.gov/health-information/communication-programs/nkdep/laboratoryevaluation/glomerular-filtration-rate-calculators/children-conventional-units)
- e) Presence of severe concurrent illnesses, such as pulmonary (i.e., bronchopulmonary dysplasia), neurological, cardiovascular, metabolic, endocrine, and renal disorders, which may be congenital or acquired, that would interfere with the conduct and results of the study
- **iii.** Total Planned Enrollment 12 subjects (minimum), 16 subjects (maximum); see below for discussion of sample size.
- iv. Inclusion of Women Male and female infants will be enrolled in this study. There may be more females than males enrolled, given that BA is slightly more common in females.
- v. Inclusion of Minorities Enrollment will be open to infants of all racial and ethnic backgrounds. Minority representation will reflect the racial/ethnic diversity of patients seen at the study hospital.
- vi. Inclusion of Children This trial will only enroll infants ≤90 days old.

D. Study Implementation

i. Study Design – This is an open label, Phase 2 study of seven days of intravenous NAC treatment after KP. Subjects will be followed for the first two years of life, and no additional clinic visits or testing beyond those routinely performed for routine BA clinical care at Texas Children's Hospital will be performed.

ii. Study Procedure

- a) Before KP
 - (1) Identify cholestatic infants likely to have BA who fulfill inclusion criteria
 - (2) Approach parent(s)/guardian(s) and explain study
- b) After KP until hospital discharge (typical length-of-stay 10-14 days)
 - (1) Consent parent(s)/guardian(s) and answer any remaining questions

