 - (2) Initiate continuous intravenous NAC therapy (6.25 mg/kg/hour of 10 mg/ml solution, or 0.625 ml/kg/hour, to give 150 mg/kg/day) within 24 hours of completion of KP (initiation to occur in pediatric intensive care unit, where all patients are admitted for observation after KP)
 - (3) Continue therapy for a total of seven days
 - (4) Collect results from laboratory tests drawn as part of standard clinical care
 - (5) Monitor for adverse events (including serious adverse events)
- c) After hospital discharge until 28 days post-KP (1) Monitor for adverse events
- d) After hospital discharge until two years of life
 - (1) Collect laboratory test results and weights measured as part of standard clinical care
 - (2) Monitor for sentinel events related to progression of liver disease (cholangitis, development of ascites, variceal bleed, liver transplant listing, liver transplant, death)
 - (3) Monitor for serious adverse events
- **iii. Consent Procedures** Parent(s)/guardian(s) will be approached before intraoperative cholangiogram/KP, and hence before the BA diagnosis is definitively made (information given but no signatures no obtained). While the KP is being performed, the study team will obtain formal consent.

iv. Drug Administration

- a) Dosage:
 - NAC 150 mg/kg/day intravenous infusion run continuously over 24 hours (administered through dedicated intravenous line). If the IV has to be interrupted due to common expected events during IV treatment (e.g. IV leak, etc), interruption will be noted in the subject chart with stop/re-start time and reason but not considered a protocol deviation unless the interruption lasts longer than 30 minutes. Interruptions > 30 minutes will be considered a protocol deviation. Similar dosing was used in infants/children in at least five studies:
 - Pharmacokinetic study delivering 100 mg/kg/day NAC intravenously over 21-24 hours for 1 day immediately after birth in premature infants gestational age 24-31 weeks.³⁰ No adverse events associated with NAC treatment were reported.
 - Case series delivering 100 mg/kg/day NAC intravenously over 24 hours for multiple weeks in infants ages 0-3 weeks with neonatal hemochromatosis/gestational alloimmune liver disease.³¹ No adverse events associated with treatment were reported.

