- Sentinel events during the study period related to liver disease, such as cholangitis, ascites, liver transplant listing, liver transplant, and/or death (see Data and Safety Monitoring Plan (DSMP) in Appendix)
- Adverse events in the first 28 days after KP possibly related to NAC, including rash, urticaria, pruritus, tachycardia, hypotension, vomiting, edema, anaphylaxis, and intravenous line issues (see DSMP in Appendix)
- **vi. Dose Modifications** Rules for modifying NAC infusion are as follows, based in part on prior recommendations for NAC therapy in acetaminophen toxicity (also see DSMP in Appendix):³⁵
 - a) Flushing alone, without pruritus, urticaria, or other serious signs
 - No intervention
 - Continue infusion, unless more severe signs develop
 - b) Urticaria
 - Stop infusion
 - Treat immediately with intravenous diphenhydramine (1.25 mg/kg/dose)
 - Restart infusion if symptoms resolve within 1 hour
 - c) Angioedema, hypotension, wheezing
 - Stop infusion
 - Treat with intramuscular epinephrine (0.01 mg/kg/dose), intravenous diphenhydramine (1.25 mg/kg/dose), intravenous glucocorticoid (1 mg/kg/dose), and/or inhaled albuterol, at the discretion of the clinical team
 - Do not restart infusion
 - Continue to follow patients for first two years of life, per study protocol
 - d) Elevation of ALT >700 U/L above baseline, Bc 3x above baseline, TB 3x above baseline, and/or Bc >5 mg/dL above baseline
 - Stop infusion
 - Do not restart infusion
 - Follow patients clinically until elevated ALT/Bc stabilizes/resolves
 - Evaluate for drug-induced liver injury if deemed appropriate by the clinical team, based on FDA recommendations (https://www.fda.gov/downloads/Drugs/.../guidances/UCM174090.pdf)
 - e) If a severe adverse event related to or possibly related to the study drug (see DSMP in Appendix for definition) occurs during the first 7 days of the trial, i.e., during NAC infusion, the infusion will be paused, and an emergency Data Safety Monitoring Board (DSMB) meeting will be convened. If the DSMB deems that causality is unrelated to NAC use, then the trial can be continued.

vii. Concurrent Treatments

a) Standard therapies: All standard therapies will be given during the study period, including ursodeoxycholic acid (20 mg/kg/day), fat-soluble vitamins (AquADEK, 1 ml once or twice daily), and up to one year of post-KP antibiotics (trimethoprim/sulfamethoxazole 5 mg/kg/day). In infants found

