to have low Vitamin A levels (<20 mcg/dL), intramuscular Vitamin A injections of 50,000 IU will be given two days before KP and 28 days after KP. Steroids will not be used as standard post-KP care.

b) Experimental therapies: No other investigational therapies will be given during the study period.

viii. Removal of Patients from Study

- a) Parents may voluntarily exclude their infant from the study at any time
- b) The investigators may remove a patient if the study team decides that continuation is not in the best interest of the participant of the study (i.e., patient receives another experimental therapy during the two-year study period that will confound the results).

E. Data Collection

- i. Clinical Data All clinical data (laboratory results, weights, occurrence of sentinel events) will be stored in the patient's electronic medical record. In addition, a comprehensive study form containing all data for each subject will be updated as new results become available.
- ii. Adverse Events All adverse events (observed by the study team, reported by parents, and/or detected by laboratory findings) will be recorded in the patient's medical record as well as separate form specifically for the study. The form will be submitted to the DSMB following a pre-determined schedule (see DSMP in Appendix).

F. Statistical Considerations

i. Overview

This is a Phase 2 clinical trial using the two-stage "minimax" design described by Simon.²⁹ As a Phase 2 trial, the trial's objective is to determine whether NAC

has sufficient biological activity as adjunctive therapy for BA to warrant further study. By choosing the two-stage "minimax" design, we gain two advantages: (i) early termination if the drug is not efficacious, and (ii) using historical controls and therefore an overall smaller sample size to test the hypothesis, i.e., no randomization or control arm. This study design only identifies large effects (response >20%). For BA this is appropriate, because the field is in need of a robust therapy that can substantially limit liver damage and delay/prevent need for liver transplantation.

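### Discretionary replacement of non-completers in an open-label trial lets failures leave the 12/16 count, so the stated 5% type I error is not guaranteed

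*Combined protocol and SAP*

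**What the plan says.** Section F.ii sets a Simon two-stage minimax design: null rate 5%, alternative 25%, stop at 0 of 12, otherwise go to 16 and reject at 3 or more. The stated type I error is 5% and the stated power 80%. The section ends with the replacement rule: "Subjects that do not complete the 7 day NAC infusion after the Kasai operation and 24 weeks of follow up may be replaced". The decision is left open: they "may be replaced at the discretion of the PI/IND Sponsor".

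Four other places bear on how that rule works:

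- **Endpoint** (D.v, primary outcomes): "Any normal TSBA (0-10 umol/L) in the first 24 weeks after KP". One normal value at any time in the window is a response.
- **Blinding** (D.i): "This is an open label, Phase 2 study of seven days of intravenous NAC treatment after KP". Section E.i adds that each subject's study form is updated as results arrive.
- **Routes to non-completion.** D.vi(d) ends the infusion for "Elevation of ALT >700 U/L above baseline, Bc 3x above baseline, TB 3x above baseline, and/or Bc >5 mg/dL above baseline". D.viii(b) says "The investigators may remove a patient if the study team decides that continuation is not in the best interest". D.ii(d) has the team "Monitor for sentinel events related to progression of liver disease", a list that includes transplant and death.
- **Enrolment** (C.iii): "12 subjects (minimum), 16 subjects (maximum"). It does not say whether replaced infants count toward the 16.

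The text available to us defines no analysis population and gives no rule for a missing primary outcome.

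**The concern.** The two Simon boundaries have their stated error rates only if the infants counted are an unselected series of those treated. F.ii names who can be replaced (non-completers) but leaves three things open: which of them are replaced, when the decision is made relative to TSBA results, and how a replaced infant is counted. The word joining the infusion and the follow-up period also leaves unclear whether missing one part is enough or both must be missed.

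The endpoint makes this one-sided. A non-completer with an early normal TSBA is already a responder, and there is no reason to replace that infant. A non-completer without one is a pending failure, and the person deciding can see this. Some routes to non-completion are also plausibly linked to poor bile flow: infusion stopped for rising ALT or bilirubin, death, or removal by the investigators. Others, such as lost intravenous access or parental withdrawal, need not be.

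If replacement follows outcome, both the futility stop and the final test refer to a response rate higher than the true rate among treated infants. The bias favours NAC in a trial with no control arm to reveal it.

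**Working it through.** **Inputs from F.ii:** null rate p = 0.05; alternative 0.25; n1 = 12, stop at 0; n = 16, reject at 3 or more. No non-completion rate is given, so every replacement rate below is an assumption.

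**1. Reproduce the design.** P(reject) = P(X1=1)·P(X2≥2) + P(X1=2)·P(X2≥1) + P(X1≥3), with X1 ~ Bin(12, p) and X2 ~ Bin(4, p).

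- At p = 0.05: 0.3413 × 0.0140 + 0.0988 × 0.1855 + 0.0196 = 0.0048 + 0.0183 + 0.0196 = **0.0427**. The stage-1 stop probability is 0.95^12 = **0.540**.
- At p = 0.25: 0.1267 × 0.2617 + 0.2323 × 0.6836 + 0.6093 = **0.801**.

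The plan's figures hold. The 5% is a ceiling, and the discrete design leaves 5.00 − 4.27 = 0.73 percentage points of slack.

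**2. Replace a share q of non-responders and no responders.** The rate among counted infants becomes p* = 0.05 / [0.05 + 0.95(1 − q)].

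| q | p* | Type I error | Stage-1 stop |
|---|---|---|---|
| 0 | 0.0500 | 4.27% | 54.0% |
| 0.05 | 0.0525 | 4.8% | 52.4% |
| 0.10 | 0.0552 | 5.5% | 50.6% |
| 0.15 | 0.0583 | 6.2% | 48.6% |
| 0.20 | 0.0617 | 7.2% | 46.6% |
| 0.30 | 0.0699 | 9.6% | 41.9% |

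If 10, 20 or 30% of non-responders fail to complete but only half of them are replaced, the rows q = 0.05, 0.10 and 0.15 apply: 4.8, 5.5 and 6.2%. Type I error passes 5% at q = 0.0647, which is 0.95 × 0.0647 = 6.1% of all infants.

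**3. Replace all non-completers, when non-completion is linked to outcome.** Suppose 20% of non-responders and 10% of responders are lost and every one is replaced. Then p* = (0.05 × 0.9) / (0.05 × 0.9 + 0.95 × 0.8) = 0.045 / 0.805 = 0.0559, and type I error is 5.6%. No selective choice is involved.

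**4. A fixed number of swaps, each used as favourably as possible.** Swapping out k first-stage failures amounts to drawing 12 + k infants in stage 1. For k = 1, 2, 3, 4, type I error is 5.0, 5.8, 6.6 and 7.5%. Dynamic programming over all swap strategies gives the same maxima.

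**5. Replacement unrelated to outcome.** p* stays at 0.05 and type I error at 4.27%.

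**6. Cost of counting every treated infant.** If the stated rate holds only in completers and all non-completers count as failures, the rate is multiplied by (1 − share not completing).

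| Non-completion | Rate under alternative | Power | Rate under null | Type I error |
|---|---|---|---|---|
| 10% | 0.225 | 73% | 0.045 | 3.3% |
| 20% | 0.200 | 65% | 0.040 | 2.4% |
| 30% | 0.175 | 55% | 0.035 | 1.7% |

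**The case against.** The rule has limits. An infant who completes infusion and follow-up without a normal TSBA cannot be replaced. If both parts must be missed, an infant whose infusion is stopped but who is followed to 24 weeks cannot be replaced either. The one example of investigator removal in D.viii is receipt of another experimental therapy, not treatment failure. These points narrow the routes but do not close them: the text does not settle which reading applies, and the choice among non-completers remains open.

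The upper end of the range is unlikely. With 16 counted, q = 0.30 implies 16 × 0.285 / 0.715 = 6.4 replaced failures, or about 22 infants enrolled. The infusion falls within a typical 10 to 14 day admission and follow-up uses routine visits, so completion may be high. That is fair, and small numbers have small effects: one best-use swap gives 5.0%, two give 5.8%. But the slack is only 0.73 points.

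The data and safety monitoring plan and board charter have the board review enrolment, retention, each subject's data and primary outcome results. Replacements would probably be visible to it. No text requires its approval.

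The historical benchmark is a larger worry than a swap or two: a true background rate of 6% gives a rejection probability of 6.7% with no replacement. That stands, but it is a separate weakness that section F.i already acknowledges.

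The strongest point is that a pre-set, outcome-independent replacement rule would preserve both type I error and power, so barring replacement of treated infants goes too far. This works only if non-completion itself is unrelated to outcome. Step 3 shows that a mechanical rule replacing every non-completer still gives 5.6% when it is not.

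**Conclusion.** The concern holds and should be fixed. As written, F.ii does not guarantee its 5% type I error. The claim is conditional: nothing in the documents shows that selective replacement has happened or will happen, and replacement unrelated to outcome does no harm. Under outcome-linked replacement the error moves from 4.27% to about 5 to 7% for one to four swaps or up to 20% of non-responders replaced, and to 9.6% at the unlikely 30%. The chance of stopping a drug with a 5% response rate at stage 1 falls from 54% to 47% at 20% and 42% at 30%. All of these rest on assumed replacement rates and a true rate of exactly 5%.

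**What to change.** Replace the last sentence of F.ii with a counting rule:

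- Every infant who starts NAC counts toward the 12 and the 16, in enrolment order.
- An infant with no normal TSBA by 24 weeks is a non-responder, whatever the reason. An infant with a normal value before leaving is a responder.
- Only infants who never start NAC may be replaced.

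Report completers as a sensitivity analysis. Disclose any replacements already made and count the replaced infants in the primary analysis. State in C.iii whether 16 means treated infants.

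This is a one-paragraph amendment and changes no dose, schedule or clinical rule. The cost is the power loss in step 6, if the 25% rate applies only to completers. The 5% benchmark comes from measured TSBA values, so scoring unmeasured infants as failures is somewhat conservative. The completer analysis gives context for that but does not restore power to the primary decision. If the sponsor finds the loss too great, the sample size should be recalculated with an explicit non-completion allowance.
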